6.2. Enrolled Set [ENR]

All eligible participants who received a study vaccine or had a blood draw before study vaccine administration or were randomized. Note that as per Good Clinical Practice (GCP) enrolled participants should have completed the informed consent process and participants should be eligible before initiating any study procedure.

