9.3. Populations for Analyses

Populations for analyses in this study are defined in Table 19.

Table 19 Study Analyses Sets

Analysis set	Description				
Enrolled set	Participants who received a study vaccine or had a blood draw before study vaccine administration or were randomized. Note as per Good Clinical Practice (GCP) enrolled participants should have completed the informed consent process and participants should be eligible before initiating any study procedure.				
Exposed set (ES)	All participants who received a study vaccine. Analysis per group is based on the study vaccine administered.				
	A safety analysis based on the ES will include all vaccinated participants. An immunogenicity analysis based on ES will include all vaccinated participants for whom immunogenicity data are available.				
Per Protocol set (PPS)	The per protocol set for analysis of immunogenicity will be defined by time point (to include all eligible participants' data up to the time of important protocol deviations).				
	The PPS will include all evaluable participants in the ES:				
	Meeting all eligibility criteria.				
	• For whom the administration route of the vaccine was as according to protocol.				
	For whom the study vaccine was administered as per protocol.				
	Who did not receive a concomitant medication/product leading to exclusion from a PP analysis, as described in the protocol.				
	Who did not present with a intercurrent medical condition leading to exclusion from a PP analysis, as described in the protocol.				

Analysis set	Description
	 Who complied with the vaccination schedule, as specified in Table 1. Who complied with the timings of the post-vaccination blood sampling for immune response evaluation, as specified in Table 1.
	 For whom post-vaccination immunogenicity results are available for at least one antigen at the corresponding time points.

For discontinuation of study intervention and participant discontinuation/withdrawal details, see Section 7.

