Caregiver In the context of a clinical study, a caregiver could include

an individual appointed to oversee and support the participant's compliance with protocol specified

procedures.

Page 69 of 110

Child in care

A child who has been placed under the control or protection of an agency, organization, institution or entity by the courts, the government or a government body, acting in accordance with powers conferred on them by law or regulation. The definition of a child in care can include a child cared for by foster parents or living in a care home or institution, provided that the arrangement falls within the definition above. The definition of a child in care does not include a child who is adopted.

Combination product

Combination product comprises any combination of

- drug
- device
- biological product

Each drug, device, and biological product included in a combination product is a constituent part.

Eligible (participant)

Qualified for enrollment into the study based upon strict adherence to inclusion/exclusion criteria.

Enrolled (participant)

"Enrolled" means a participant's/participant's parent(s)'/LAR(s)' agreement to participate in a clinical study following completion of the informed consent process. Potential participants who are evaluated for the purpose of determining eligibility for the study, but do not participate in the study, are not considered enrolled, unless otherwise specified by the protocol.

Essential documents

Documents which individually and collectively permit evaluation of the conduct of a study and the quality of the data produced.

Evaluable (participant)

Meeting all eligibility criteria, complying with the procedures defined in the protocol, and, therefore, included in the per protocol analysis.

Immunological correlate

of protection

Intercurrent medical Conditions

A correlate of risk that has been validated to predict a certain level of protection from the targeted endpoint.

A condition that has the capability of altering a participant's immune response including an

immunodeficiency condition diagnosed during the study.

Intervention

Term used throughout the clinical study to denote a set of investigational product or marketed product or placebo intended to be administered to a participant.

Page 70 of 110

Invasive medical device A device wh

A device which, in whole or in part, penetrates inside the body, either through a body orifice or through the surface of the body.

Investigational vaccine/product

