7. GENERAL CONSIDERATIONS

Data will be summarized descriptively (frequency and percentage for categorical data and mean, standard deviation [SD] and range for continuous data, unless specified otherwise). In summary tables for categorical data for which categories are defined on the eCRF, all categories will be presented as specified, even if the participant count within that category is zero.

Unless otherwise specified, all data collected during the trial will be presented in listings for the ENR.

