Output ID: LS0001

[Source: \\quintiles.net\Enterprise\Apps\sasdata\SASb\SAS\GlaxoSmithKline\HPV\213749

(HPV9) \Biostatistics\Filename.sas] IQVIA DDMMMYYYY HH:MM

\\quintiles.net\Enterprise\Apps\sasdata\SASb\SAS\GlaxoSmithKline\HPV\213749 (HPV9)\Biostatistics\Documentation\SAP\Shells\ Document: GSK 213749(HPV9-AS04-001)_WZA97329_TFL Shells_V3.0_05FEB2024.docx

Version Number: 3.0 Author: Version Date: 05FEB2024

Listing 16.2.1.2: Participants with Early Withdrawal or Discontinuation due to COVID-19 (Enrolled Set)

GSK Vaccines Page X of Y

Study 213749 - DELIVERY DESIGNATION

Listing 16.2.1.2 Participants with Early Withdrawal or Discontinuation due to COVID-19 Enrolled Set

Vaccine Group: HPV9 High / HPV9 Medium / HPV9 Low / Gardasil 9

Participant Identifier	Site ID	Discontinue Treatment due to COVID-19	Discontinue Study due to COVID-19
	XX	Yes	Yes
XXXXXXX	XX	No	No

Abbreviations: HPV = Human Papillomavirus. COVID-19 = Coronavirus disease 2019.

Programming Notes

Output ID: LS0002

[Source: \quintiles.net\Enterprise\Apps\sasdata\SASb\SAS\GlaxoSmithKline\HPV\213749

(HPV9) \Biostatistics\Filename.sas] IQVIA DDMMMYYYY HH:MM

Document: \(\quintiles.net\Enterprise\Apps\sasdata\SASb\SAS\GlaxoSmithKline\HPV\213749\) (HPV9)\Biostatistics\Documentation\SAP\Shells\\
GSK\\\ 213749\(\text{HPV9-AS04-001}\) \(\text{WZA97329}\) \(\text{TFL Shells}\\\ \text{V3.0}\) \(\text{05FEB2024.docx}\)

Author: Version Number: 3.0

Listing 16.2.1.3: Participant Analysis Set (Enrolled Set)

GSK Vaccines Page X of Y

Study 213749 - DELIVERY DESIGNATION

Listing 16.2.1.3
Participant Analysis Set
Enrolled Set

Vaccine Group: HPV9 High / HPV9 Medium / HPV9 Low / Gardasil 9

Participant Identifier	Site ID	Date; Time of Informed Consent	Enrolled Set (ENR); If no, reason for exclusion	Exposed Set (ES); If no, reason for exclusion	Per Protocol Set (PPS); If no, reason for exclusion
xxxxxxx	xx	ddmmmyyyy; hh:mm	Yes No; xxxxxx	Yes No; xxxxxx	Yes No; xxxxxx

Abbreviations: HPV = Human Papillomavirus.

Programming Notes

Output ID: LS0003

[Source: \\quintiles.net\Enterprise\Apps\sasdata\SASb\SAS\GlaxoSmithKline\HPV\213749

Author: Version Number: 3.0

Listing 16.2.1.4: Inclusion and Exclusion Criteria at Enrolment (Enrolled Set)

GSK Vaccines Page X of Y

Study 213749 - DELIVERY DESIGNATION

Vaccine Group: HPV9 High / HPV9 Medium / HPV9 Low / Gardasil 9

Participant		Inclusion/ Exclusion	
Identifier	Site ID	Category Failed	Criteria Failed
XXXXXXX	XX	Inclusion	xxxxxxxxxxxxxx
		Exclusion	

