Abbreviations: HPV = Human Papillomavirus.

Programming Notes

Output ID: LS0004

[Source: \\quintiles.net\Enterprise\Apps\sasdata\SASb\SAS\GlaxoSmithKline\HPV\213749

(HPV9)\Biostatistics\Filename.sas| IOVIA DDMMMYYYY HH:MM

Document: \(\quintiles.net\Enterprise\Apps\sasdata\SASb\SAS\GlaxoSmithKline\HPV\213749\) (HPV9)\Biostatistics\Documentation\SAP\Shells\\ GSK\\ 213749\) (HPV9-AS04-001)\(\quintiles\text{WZA97329_TFL\ Shells\\ V3.0_05FEB2024.docx\)

Author: Version Number: 3.0

Listing 16.2.2.1: All Protocol Deviations (Enrolled Set)

GSK Vaccines Page X of Y

Study 213749 - DELIVERY DESIGNATION

Listing 16.2.2.1 All Protocol Deviations Enrolled Set

Vaccine Group: HPV9 High / HPV9 Medium / HPV9 Low / Gardasil 9

Participant Identifier	Site ID	Classification	Date of Deviation	Deviation Category	Description	Exclusion from Per Protocol Set?
xxxxxxx	XX	Important Not important	ddmmmyyyy ddmmmyyyy	Inclusion: xxxxxxxxxxxxxxxxxxxxxxxxxxxxxxxxxxxx	Xxxxxxxxxxxx	Yes No

Abbreviations: HPV = Human Papillomavirus.

Programming Notes

Output ID: LS0005

[Source: \quintiles.net\Enterprise\Apps\sasdata\SASb\SAS\GlaxoSmithKline\HPV\213749

(HPV9) \Biostatistics\Filename.sas] IQVIA DDMMMYYYY HH:MM

\\quintiles.net\Enterprise\Apps\sasdata\SAS\SAS\GlaxoSmithKline\HPV\213749 (HPV9)\Biostatistics\Documentation\SAP\Shells\ Document: GSK 213749(HPV9-AS04-001)_WZA97329_TFL Shells_V3.0_05FEB2024.docx

Version Number: 3.0 Author: Version Date: 05FEB2024

Listing 16.2.4.1: Demographics and Other Baseline Characteristics (Enrolled Set)

GSK Vaccines Page X of Y

Study 213749 - DELIVERY DESIGNATION

Listing 16.2.4.1 Demographics and Other Baseline Characteristics Enrolled Set

Vaccine Group: HPV9 High / HPV9 Medium / HPV9 Low / Gardasil 9

Participant	Site	Age	Year of			
Identifier	ID	(years)	Birth	Sex	Race	Ethnicity
xxxxxxx	XX	xx	УУУУ	Female	Black or African American	Hispanic of Latino
		XX	УУУУ		American Indian or Alaska Native	Not Hispanic o Latino
		xx	УУУУ		Asian Native Hawaiian or other Pacific Islander White Other	

Abbreviations: HPV = Human Papillomavirus.

Programming Notes

Output ID: LS0006

[Source: \\quintiles.net\Enterprise\Apps\sasdata\SASb\SAS\GlaxoSmithKline\HPV\213749

(HPV9)\Biostatistics\Filename.sas| IOVIA DDMMMYYYY HH:MM

\\quintiles.net\Enterprise\Apps\sasdata\SASb\SAS\GlaxoSmithKline\HPV\213749 (HPV9)\Biostatistics\Documentation\SAP\Shells\ Document: GSK 213749(HPV9-AS04-001)_WZA97329_TFL Shells_V3.0_05FEB2024.docx

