Vaccine Group: HPV9 High / HPV9 Medium / HPV9 Low / Gardasil 9 Potential Start Date System Organ (Onset Action Immune-Mediated Class; Day); End Taken to Severity; Treatment Preferred Term; Date Relationship Study Disease Serious; Given? If Participant Site (Study Duration to Study Drug; (DMIq) If yes, Medical AE term Yes, Identifier ID (Vaccine Dose) Day) (Days) Treatment Outcome event? Criteria Attention COVID19? Treatment Mild / ddmmmyyyy Yes No xxxxxx; Moderate/ (x); XXXXXXXX XXXXXXXXXX; Severe; XXXXXXX XX xxxxxxxxx; ddmmmyyyy XX Yes Yes; xxxx Yes Related / xxxxxx (x) (x) Not Related No No No Yes; xxxx

Abbreviations: HPV = Human Papillomavirus. COVID19 = Coronavirus disease 2019. MedDRA = Medical dictionary for regulatory activities.

MedDRA version xx.x.

Unsolicited AEs include serious AEs.

Programming Notes

Output ID: LS0016

[Source: \quintiles.net\Enterprise\Apps\sasdata\SASb\SAS\GlaxoSmithKline\HPV\213749

(HPV9)\Biostatistics\Filename.sas| IOVIA DDMMMYYYY HH:MM

Document: \\quintiles.net\Enterprise\Apps\sasdata\SASb\SAS\GlaxoSmithKline\HPV\213749 (HPV9)\Biostatistics\Documentation\SAP\Shells\

GSK 213749(HPV9-AS04-001) WZA97329 TFL Shells V3.0 05FEB2024.docx

Author: Version Number: 3.0

Listing 16.2.7.5: Serious Adverse Events (Enrolled Set)

GSK Vaccines Page X of Y

Study 213749 - DELIVERY DESIGNATION

Listing 16.2.7.5 Serious Adverse Events Enrolled Set

Vaccine Group: HPV9 High / HPV9 Medium / HPV9 Low / Gardasil 9

		System Organ Class;		
Participant		Preferred Term;		
Identifier	Site ID	AE Term (Vaccine Dose)	Country	
				•
		xxxxxxxxxxxxxxx;		
		xxxxxxxxxxxxxx;		
XXXXXXX	XX	xxxxxxxxxxxxx (x)	XXXXXXXXX	

Abbreviations: HPV = Human Papillomavirus. Serious AEs are expedited adverse events.

Programming Notes

Output ID: LS0017

[Source: \quintiles.net\Enterprise\Apps\sasdata\SASb\SAS\GlaxoSmithKline\HPV\213749

(HPV9) \Biostatistics\Filename.sas] IQVIA DDMMMYYYY HH:MM

\\quintiles.net\Enterprise\Apps\sasdata\SASb\SAS\GlaxoSmithKline\HPV\213749 (HPV9)\Biostatistics\Documentation\SAP\Shells\ Document: GSK 213749(HPV9-AS04-001)_WZA97329_TFL Shells_V3.0_05FEB2024.docx

Version Number: 3.0 Author: Version Date: 05FFB2024

Listing 16.2.7.6: All Serious Adverse Events Leading to Withdrawal or Discontinuation from Study (Enrolled Set)

GSK Vaccines Page X of Y

Study 213749 - DELIVERY DESIGNATION

Vaccine Group: HPV9 High / HPV9 Medium / HPV9 Low / Gardasil 9

Participant		System Organ Class; Preferred Term;		

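### SAP 6.2 restricts the Enrolled Set to eligible participants and Protocol Table 19 does not; applied literally, this breaks participant accounting and table-to-listing tracing

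*SAP*

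**What the plan says.** Protocol 9.3, Table 19, defines the Enrolled Set as "Participants who received a study vaccine or had a blood draw before study vaccine administration or were randomized". A note beneath it says that, under GCP, enrolled participants should have consented and should be eligible before any procedure. The note states what is expected; it is not a membership condition.

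SAP 6.2 keeps the three routes into the set and the GCP note, but opens differently: "All eligible participants who received a study vaccine or had a blood draw before study vaccine administration or were randomized". The protocol glossary (Appendix 1) defines an eligible participant as "Qualified for enrollment into the study based upon strict adherence to inclusion/exclusion criteria". SAP 4.3, which lists departures from the protocol's analysis, does not mention this one.

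The set is used widely. SAP 7 states: "Unless otherwise specified, all data collected during the trial will be presented in listings for the ENR". In the shells, the Enrolled Set is the named population for disposition (Table 14.1.1.1), important deviations (Table 14.1.6), failed inclusion and exclusion criteria (Listing 16.2.1.4), all protocol deviations (Listing 16.2.2.1) and serious adverse events (Listing 16.2.7.5).

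The Exposed Set (SAP 6.3) is everyone vaccinated, with no eligibility condition. SAP 17.1.3 and 17.2 place the safety analyses on that set.

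**The concern.** An enrolled set normally contains everyone who entered the trial, and the exposed and per-protocol sets are carved out of it in turn. A condition at the top that is absent from the next set down breaks that nesting. SAP 6.1 says participants are assigned to sets by the SAP's own definitions, so a programmer would follow 6.2 rather than the protocol.

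The women at issue are those randomized or vaccinated and later found not to have met a criterion. That is plausible here. Protocol 5.3 says there is no screening phase, and several exclusions in Protocol 5.2 rest on history, such as earlier HPV vaccination, an abnormal Papanicolaou test or genital warts. If such a woman had a serious adverse event, it would be counted in an Exposed Set table with no matching row in the listing, and the disposition table would not include her.

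**Working it through.** The plan states no figure on this point, so the check is a comparison of texts followed by tracing one woman through the outputs.

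**Step 1: the definitions.** Protocol Table 19 and SAP 6.2 share the routes of vaccination, a pre-vaccination blood draw, or randomization. Only the SAP adds eligibility. SAP 10 describes enrolled participants by vaccination or randomization. It leaves out the blood-draw route, a separate small difference, but it too sets no eligibility condition, and it promises that all of them will be accounted for. SAP 10.1 wants reasons for exclusion, including failed inclusion and exclusion criteria, shown on the Enrolled Set. SAP 6.4 applies eligibility as a filter inside the Exposed Set, which presupposes that an ineligible woman can have been vaccinated.

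**Step 2: trace a vaccinated woman later found ineligible,** using the glossary meaning.

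| Set or output | Population | Protocol Table 19 | SAP 6.2, literal |
|---|---|---|---|
| Enrolled Set | n/a | in | out |
| Exposed Set | n/a | in | in |
| Per Protocol Set | n/a | out | out |
| Table 14.3.1.7 (SAEs), if she had one | Exposed | counted | counted |
| Table 14.1.2 (eliminations, with inclusion and exclusion criteria rows) | Exposed | counted | counted |
| Table 14.1.1.1 (disposition) | Enrolled | counted | missing |
| Table 14.1.6 (important deviations) | Enrolled | counted | missing |
| Listing 16.2.7.5 (SAEs), if she had one | Enrolled | shown | missing |
| Listing 16.2.2.1 (all deviations) | Enrolled | shown | missing |
| Listing 16.2.1.4 (failed criteria) | Enrolled | shown | missing |

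**Step 3: nesting.** Let V and U be the vaccinated and unvaccinated women meeting Protocol Table 19, with subscripts e (eligible) and i (ineligible).

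- Protocol Enrolled Set = V_e + V_i + U_e + U_i, which always contains the Exposed Set, V_e + V_i.
- SAP 6.2 Enrolled Set, literal = V_e + U_e, which does not contain the V_i women.
- Disposition would report V_e vaccinated, while the safety tables use V_e + V_i, a gap of V_i.
- Table 14.1.3 shows the exposed count as a percentage of the Enrolled Set. If the whole Exposed Set is counted, that is 100 × (V_e + V_i) / (V_e + U_e), which exceeds 100% whenever V_i > U_e.
- Ineligible, unvaccinated women (U_i) would be in neither set, although SAP 10 promises to account for everyone randomized.

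Neither document gives V_i or U_i. With *eligible* deleted, the last two columns of the table agree in every row.

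**The case against.** The strongest reply is that this is a drafting slip that nobody would program. SAP 10 and 10.1 treat the Enrolled Set as including eligibility failures. The shell for Listing 16.2.1.4 has a column for the failed criterion, so its authors expected entries. Listing 16.2.1.3 is titled for the Enrolled Set, yet allows *no* as the answer to Enrolled Set membership, so the shells do not treat the label as a strict filter. This stands in part: the losses in the table are conditional on literal use. A reader might infer that Listing 16.2.1.4 is bound to be empty, or that disposition will certainly omit randomized women. The documents do not support that certainty, because other SAP sections point the other way.

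A second reply is that *eligible* may mean judged eligible at entry. Protocol 6.3.2 and 6.3.3 speak of randomizing eligible participants after an eligibility check, and on that usage women later found in violation remain in the set. The glossary's strict-adherence wording favours the other sense. What remains is ambiguity in an operative definition, which still needs resolving.

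A third reply is that the information appears elsewhere. Table 14.1.2 is on the Exposed Set and has inclusion and exclusion criteria rows. SAP 10.2 puts the important-deviation summary on the Exposed Set, which differs from the Table 14.1.6 shell and is a separate mismatch. SAP 6.1 requires sponsor review of everyone excluded from each set, where a dropped vaccinated woman would probably be noticed. All of this limits the damage; none of it makes SAP 6.2 agree with the protocol.

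**Conclusion.** The inconsistency is real and minor. SAP 6.2 contradicts Protocol Table 19 without declaring the change, and it contradicts SAP 10 and 10.1. Applied as written, it would give wrong participant accounting and would leave some table counts without a source row in the listings.

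This rests on three assumptions: the SAP 6.2 definition is programmed literally, *eligible* carries its glossary meaning, and at least one randomized or vaccinated woman is later found ineligible. The number of such women is not given, so no magnitude can be attached.

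A reader might go further and infer that ineligible women, or their serious adverse events, drop out of the safety analysis. They do not: the solicited, unsolicited, serious and immune-mediated event tables use the Exposed Set, and Protocol 9.4.2.1 also calls for serious and immune-mediated events to be described in detail. Nor does any immunogenicity endpoint move. The Per Protocol Set already requires eligibility, and it is drawn from the Exposed Set rather than the Enrolled Set.

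**What to change.** Delete *eligible* from the first sentence of SAP 6.2 so that it matches Protocol Table 19. This removes the conflict with SAP 10 and 10.1 and nests the Exposed Set in the Enrolled Set again. The GCP note can stay as it is. The cost is one word, with no change to data collection, design, shells or any endpoint analysis.

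If the restriction is intended, declare and justify it in SAP 4.3, define the word, and move Tables 14.1.1.1 and 14.1.6 and Listings 16.2.1.4, 16.2.2.1 and 16.2.7.5 to all randomized or vaccinated participants. That is more work for no evident gain.

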6.3. Exposed Set [ES]

All participants who received a study intervention. Analysis per group is based on the study vaccine administered

6.4. Per Protocol Set [PPS]

A per-protocol set (PPS) will be defined for all participants in the ES at each visit that meet the following criteria:

- Meeting all eligibility criteria
- For whom the administration route of the vaccine was as according to protocol
- For whom the study vaccine was administered per protocol
- Who did not receive a concomitant medication/product/vaccine leading to exclusion from a PP analysis, as
 described in the protocol
- Who did not present with an intercurrent medical condition leading to exclusion from a PP analysis, as described in the protocol
- Who complied with the vaccination schedule
- Who complied with the timings of the post-vaccination blood sampling for immune response evaluation
- For whom post-vaccination immunogenicity results are available for at least one antigen at the corresponding time points

The eliminations for the PPS will be adapted as per the timepoint analysis, e.g., for month 3 analysis only violations up to month 3 will be excluded.

Document: \\quintiles.net\Enterprise\Apps\sasdata\SAS\\SAS\GlaxoSmithKline\HPV\213749

(HPV9)\Biostatistics\Documentation\SAP\GSK_213749(HPV9-AS04-

001)_WZA97329_SAP_Final_v3.0_02FEB2024.docx

Author: PPD Version Number: 3.0

Version Date: 02FEB2024

Template No.: CS_TP_BS016 Revision 7 Reference: CS_WI_BS005

Page 26 of 48

7. GENERAL CONSIDERATIONS

Data will be summarized descriptively (frequency and percentage for categorical data and mean, standard deviation [SD] and range for continuous data, unless specified otherwise). In summary tables for categorical data for which categories are defined on the eCRF, all categories will be presented as specified, even if the participant count within that category is zero.

Unless otherwise specified, all data collected during the trial will be presented in listings for the ENR.

7.1. Reference Start Date and Study Day

Study Day will be calculated from the reference start date and will be used to show start/stop day of assessments and events.

Reference start date is defined as the day of the most recent dose of study vaccination and will appear in every listing where an assessment date or event date appears.

If the date of the event is on or after the date of vaccination then:

Study Day = (date of event – date of vaccination) + 1.

If the date of the event is prior to the date of vaccination then:

Study Day = (date of event – date of vaccination).

In the situation where the event date is partial or missing, Study Day, and any corresponding durations will appear partial or missing in the listings.

7.2. Baseline

Unless otherwise specified, baseline is defined as the last non-missing measurement taken prior to reference start date (including unscheduled assessments). In the case where the last non-missing measurement and the reference start date coincide, that measurement will be considered baseline if the assessment is planned per protocol to take place prior to first study vaccination administration. Adverse Events (AEs) and medications commencing on the reference start date will be considered post-baseline unless otherwise indicated based on available start date/time

Document: \\quintiles.net\Enterprise\Apps\sasdata\SAS\\SAS\GlaxoSmithKline\HPV\213749

(HPV9)\Biostatistics\Documentation\SAP\GSK 213749(HPV9-AS04-

001)_WZA97329_SAP_Final_v3.0_02FEB2024.docx

Author: PPD Version Number: 3.0

Version Date: 02FEB2024

Template No.: CS_TP_BS016 Revision 7 Reference: CS_WI_BS005

Page 27 of 48

combination or collected eCRF information that identifies the individual event/medication as starting prior to first study vaccination administration.

